#### **7.3.3 Compliance**

Patient's compliance will be described by treatment groups.

#### **7.3.4 Vital Signs Data**

Vital signs data such as blood pressure, heart rate and body temperature will be summarized as continuous data by treatment group.

All vital signs data and changes from baseline will be described at each visit.

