3.3.4 Significant Potential Risks

Levopront® is a drug of Dompe Farmaceutici S.p.A., Italy, authorized in European Union and in extra European countries (Brazil, Mexico, Chile Columbia, Costa Rica, Ecuador, El Salvador, Guatemala, Honduras, Indonesia, Nicaragua, Panama, Philippines, Thailand, Venezuela, Turkey, South Korea), and established within the past two decades as a reliable and safe cough agent. Potential risks (known side effects) of Levopront® include:

Eye disorders: Mydriasis, bilateral blindness.

Immune system disorders: Allergic and anaphylactoid reactions, eyelid edema, angioneurotic edema, urticaria.

Psychiatric disorders: Nervousness, drowsiness, personality change, or personality disorder.

Nervous system disorders: Syncope, dizziness, vertigo, tremor, paraesthesia, tonic-clonic seizures and attacks of petit mal, hypoglycemic coma.

Cardiac disorders: Palpitations, tachycardia, atrial bigeminy.

Vascular disorders: Hypotension.

Respiratory, thoracic and mediastinal disorders: Dyspnea, cough, edema of the respiratory tract.

Gastrointestinal disorders: Gastric pain, abdominal pain, nausea, vomiting, diarrhea.

Hepatobiliary disorders: Cholestatic hepatitis.

Skin and subcutaneous tissue disorders: Urticaria, erythema, rash, pruritus, angioedema, skin reactions, aphthous stomatitis and glossitis. Epidermolysis.

Musculoskeletal and connective tissue disorders: Weakness of the lower limbs.

General disorders and conditions regarding the side of administration: General malaise, generalized edema, asthenia.

Preclinical study results have shown that the drug after acute and chronic dosing for 3 months has no toxic effects in warm-blooded laboratory animals (rodent and non-rodent species – rabbits), including developing organisms.

Potential risks of Libexin® include: hypersensitivity reactions: bronchospasm, skin rash, angioedema; GI tract disorders: dry mouth and throat, transient numbness and loss of sensitivity of the oral mucosa, stomach ache, predisposition to constipations, nausea; nervous system disorders: light sedative effect, fatigue (sedative effect and fatigue are observed at doses exceeding therapeutic, and all symptoms spontaneously resolve within several hours after drug discontinuation).

The study will include only the patients who agree to use adequate contraception measures for the whole study period.

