Particular attention in the study will be paid to adverse events on the part of essential organs according to subjective complaints, physical examination, vital signs, laboratory test results, and ECG.

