7 STUDY PROCEDURES

7.1 Screening and Randomization

7.1.1 Visit 1, Day 1

- Procedure of obtaining Informed Consent
- Patient registration
- Collection of demographic data, medical history and concomitant therapy
- Assessment of the severity and frequency of daytime and nighttime cough according to "Six-point daytime and nighttime cough assessment scale"
- Assessment of the cough intensity with the visual-analogue scale
- Physical examination
- Vital signs
- Height, weight
- ECG (12 leads)
- Collection of blood samples for blood hematology and biochemistry
- Collection of urine sample for clinical urine analysis and pregnancy test (women of childbearing potential, including women at menopause of less than two years)
- Spirometry (pre- and post-bronchodilator use)
- Chest X-ray or fluorography
- Inclusion/exclusion criteria
- Assessment of adverse events
- Patient enrolment (After examination, obtaining ECG results, spirometry, fluorography (or X-ray) or confirming compliance to all inclusion/exclusion criteria patients will be randomized)

Patients not meeting all inclusion/exclusion criteria will not be included into the study. Patients not included into the study for manageable reasons, may once pass re-screening on agreement with the Sponsor or his/her representative.

Randomization

- Prescription and dispensing of the study drug (administration of the first dose of the study drug at the site)
- Assessment of adverse events
- Dispensing patient diaries

Patient randomization is performed before laboratory test results are available. In case of significant abnormality which, at the Investigator's, opinion could interfere with patient's participation in the study or impact interpretation of efficacy or safety parameters, the patient should be withdrawn from the study.

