7.4 Unscheduled Visits

At the Investigator's discretion patients may be invited to an unscheduled visit at any time during clinical trial for safety reasons, should repeated examination or procedure be required. At unscheduled visits the Investigator may perform the required procedures, including laboratory and instrumental studies. Unscheduled visits should be documented in the source documentation and CRF. Unscheduled visits should not modify the preplanned visit schedule per protocol.

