### 9.3 SAFETY

**Table 9.15 Physical examination. Safety population. N = xx**

Category	Levopront® (T) n (%) N = XX	Libexin® (C) n (%) N = XX	p-value
Screening (baseline). Day 1			0.xxx
General appearance			
Normal	xx (xx.x%)	xx (xx.x%)	
Abnormal	xx (xx.x%)	xx (xx.x%)	
Not done	xx (xx.x%)	xx (xx.x%)	
Eyes, ears, nose, throat			
Normal	xx (xx.x%)	xx (xx.x%)	
Abnormal	xx (xx.x%)	xx (xx.x%)	
Not done	xx (xx.x%)	xx (xx.x%)	
Neck (including thyroid)			
Normal	xx (xx.x%)	xx (xx.x%)	
Abnormal	xx (xx.x%)	xx (xx.x%)	
Not done	xx (xx.x%)	xx (xx.x%)	

Category	Levopront® (T) n (%) N = XX	Libexin® (C) n (%) N = XX	p-value
.. Day 4			0.xxx
... Day 8/ET or ED			0.xxx
...			

Table 9.16 Vital signs. Safety population. N = xx

	Levopront® (T) N = XX	Libexin® (C) N = XX
Day 1 (baseline)		
Body temperature (°C)		
N	xx	xx
Mean (SD)	xx.x (xx.x)	xx.x (xx.x)
Median	xx.x	xx.x
Min - Max	xx.x - xx.x	xx.x - xx.x
Heart rate (beats/min)		
N	xx	xx
Mean (SD)	xx.x (xx.x)	xx.x (xx.x)
Median	xx.x	xx.x
Min - Max	xx.x - xx.x	xx.x - xx.x
Respiratory rate (/min)		
N	xx	xx
Mean (SD)	xx.x (xx.x)	xx.x (xx.x)
Median	xx.x	xx.x
Min - Max	xx.x - xx.x	xx.x - xx.x
Systolic blood pressure (Hg mm)		
N	xx	xx
Mean (SD)	xx.x (xx.x)	xx.x (xx.x)
Median	xx.x	xx.x
Min - Max	xx.x - xx.x	xx.x - xx.x
Diastolic blood pressure (Hg mm)		
N	xx	xx
Mean (SD)	xx.x (xx.x)	xx.x (xx.x)
Median	xx.x	xx.x
Min - Max	xx.x - xx.x	xx.x - xx.x
Day 4		
...		
Day 4. Change from baseline		
N	xx	xx
Mean (SD)	xx.x (xx.x)	xx.x (xx.x)
Median	xx.x	xx.x
Min - Max	xx.x - xx.x	xx.x - xx.x
p-change	0.xxx	0.xxx
Day 8/ET or ED		
...		
Day 8/ET or ED. Change from baseline		
...		

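### No post-dose ECG is scheduled, and post-baseline vital signs have no between-arm estimate and no count of marked changes, so the listed tachycardia and hypotension risks rest mainly on open-label adverse event reporting

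*SAP*

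**What the plan says.** **Known risks.** Protocol 3.3.4 lists for Levopront "Cardiac disorders: Palpitations, tachycardia, atrial bigeminy" and "Vascular disorders: Hypotension". It then says that adverse events of essential organs will get particular attention, "according to subjective complaints, physical examination, vital signs, laboratory test results, and ECG".

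**ECG.** Table 1 of the protocol marks ECG at Visit 1 only. Protocol 7.1.1 places it before randomization: "After examination, obtaining ECG results, spirometry, fluorography (or X-ray) or confirming compliance to all inclusion/exclusion criteria patients will be randomized". The procedure lists for Visits 2 and 3 (7.2.1, 7.2.2) contain no ECG. A later one could arise only ad hoc, under 7.4: "At unscheduled visits the Investigator may perform the required procedures, including laboratory and instrumental studies". The SAP has no ECG section or table.

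**Vital signs.** They are taken on Days 1, 4 and 8. SAP 7.3.4 states: "Vital signs data such as blood pressure, heart rate and body temperature will be summarized as continuous data by treatment group". It adds that values and changes from baseline are described at each visit. In Table 9.16 the change block (for example "Day 4. Change from baseline") gives N, mean (SD), median and range for each arm, with one *p-change* per arm. It has no between-arm difference, interval or p-value, and no patient counts.

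**Day 8.** Protocol 5.3 and 7.2.2 put the last dose on the evening before Visit 3 and forbid study drug on the day of that visit.

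**The concern.** Patients enter with an acute infection and may take antipyretics and nasal vasoconstrictors (protocol 5.6). Pulse in particular would be expected to change as they recover, whichever drug they receive. A within-arm test cannot separate that change from a drug effect; the randomized contrast can, and it is not planned.

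The gap is out of line with the rest of the SAP. Post-baseline comparisons between arms are planned for adverse events (7.3.1), clinically significant laboratory deviations (7.3.2), physical examination (7.3.5) and FEV1 (7.2.4.5). Vital signs themselves get a between-arm p-value at baseline (Table 9.7), where randomization already makes the arms comparable in expectation, but none after dosing.

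Means also say little about a harm that affects a few patients. The range shows one extreme at each end of each arm, not how many patients lie near it. What remains is the adverse event route. Protocol 6.5 has a vital-sign change recorded as an event if it is regarded as one, gives no numeric definition, and leaves that judgement to staff who know the treatment. At stake is whether the safety report can say anything quantitative about pulse and blood pressure, which the safety endpoint (SAP 4.2) names as a data source.

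**Working it through.** The plan gives no figure for vital signs, so only the sample size can be reproduced. It supplies the number per arm used below.

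**1. Sample size (protocol 9.2).** n = (1.96 + 0.84)² × (0.21 + 0.21) / 0.20² = 82.3 per arm. Dividing by 0.90 for early discontinuation gives 91.5, rounded up to 92 per arm, 184 in all. This agrees with the protocol.

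**2. Assumptions, none from the documents.** SD of change in pulse or pressure: 8 to 15 units (8 to 12 in steps 3 and 4). Fall in pulse with recovery: 5 or 8 beats/min. Drug effect on pulse: +5 in every patient.

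**3. Within-arm test against between-arm contrast (pulse, SD 10, 92 per arm).**
- SE within an arm = 10/√92 = 1.04; SE between arms = 10 × √(2/92) = 1.47.
- Recovery -8, drug +5: Levopront mean change -3, z = -3/1.04 = -2.9; Libexin -8, z = -7.7. Both *p-change* tests report a fall.
- Recovery -5, drug +5: Levopront mean change 0; its *p-change* shows nothing.
- In both cases the between-arm z = 5/1.47 = 3.4. Over SD 8 to 12 it runs from 4.2 to 2.8.

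**4. A few affected patients.** Four patients with a 25 beats/min rise move the arm mean by 4 × 25/92 = 1.1 beats/min. The between-arm SE is 1.18, 1.47 and 1.77 at SD 8, 10 and 12, so a test of means has about 15%, 11% and 9% power. A difference in means would not show this pattern either; a count would display it. Even 4 against 0 would not be significant (two-sided Fisher p = 2 × C(92,4)/C(184,4), about 0.12), and zero cases on Libexin is itself assumed.

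**5. What the proposed contrast delivers (unadjusted, 92 per arm).** Half-width of the 95% CI = 1.96 × SD × √(2/92).

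| SD | Half-width | Power for a 5-unit difference | Power for a 3-unit difference |
|---|---|---|---|
| 8 | 2.3 | 99% | 72% |
| 10 | 2.9 | 92% | 53% |
| 12 | 3.5 | 81% | 40% |
| 15 | 4.3 | 62% | 27% |

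With 83 per arm the half-widths are 2.4, 3.0, 3.7 and 4.6.

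**6. The adverse event route.** With 92 patients, the chance of at least one case is 60% at a true rate of 1%, 84% at 2% and 99% at 5%. No case in 92 still allows a rate up to 3.2% (one-sided 95%). A Fisher test on one event type has about 53% power for 2% against 10%, and 16% for 1% against 5%. The preferred-term comparison in SAP 7.3.1 is a single p-value over all terms, so a cardiac signal would be diluted further.

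**7. Which visit is on treatment.** Day 1 readings precede the first dose, and Day 8 readings are taken with that day's drug withheld. Day 4 is therefore the only scheduled vital-signs visit on a dosing day after baseline. Its timing relative to a dose is not stated.

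**The case against.** A reader might infer that the cardiac and blood-pressure harms have no usable analysis at all, that vital signs are reduced to arm means, or that a harm would be reported as ordinary recovery. The documents do not support any of these.

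- Adverse events are asked about at every visit and logged in the diary (protocol 6.12.3). They are tabulated by arm, with a permutation test (SAP 7.3.1) and Fisher tests on summary categories (Table 9.33). Physical examination covers the heart (protocol 6.4) and is compared between arms. Palpitations and bigeminy could not be analysed from a pulse table in any case.
- Table 9.16 gives SD, median and range as well as the mean, and a large individual rise would appear as the maximum of the change row.
- Both arms stand side by side, so a reader can subtract the means. The contrast is unestimated, not hidden.
- The masking argument is worked only for pulse. Nothing here shows that recovery would hide a fall in blood pressure.
- The documents' own safety summary (protocol 3.3.2) reports 3 cases of palpitations and 1 of precordial pain in 2868 patients: 4/2868 = 0.14%, or about 0.13 expected in 92. The four-patient example is some 31 times that rate. Those are reported reactions rather than measured pulse, so the comparison is loose.
- Protocol 3.3.4 lists ECG as one source for noticing events and promises no on-treatment recording. The safety endpoint omits ECG, and an unscheduled one is possible.
- Descriptive vital signs are what protocol 9.8 specifies.

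These points limit the claim without removing it. Subtracting displayed means yields no interval, a range yields no count, and the adverse event route depends on unblinded judgement. Protocol 9.8 asks for descriptive statistics, yet Table 9.16 already goes further by adding a test, and that test addresses the wrong comparison.

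**Conclusion.** The point holds in a limited form. No ECG is scheduled after dosing, although protocol 3.3.4 names ECG as a source. Post-baseline vital signs have only per-arm descriptives and a within-arm test that confounds drug effect with recovery. Detection of the listed tachycardia and hypotension risks therefore rests mainly on open-label adverse event reporting, on the range, and on a reader subtracting two means without an interval.

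The size depends on assumed SDs, recovery and drug effects. Under them, a 5 beats/min effect could sit behind a reported fall or no change on Levopront, while the between-arm contrast would have z of 2.8 to 4.2. That establishes a risk, not an outcome. The primary and secondary efficacy conclusions are unaffected.

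The contrast is against an active drug, so an effect shared by both arms would not show. Protocol 3.3.4 lists no cardiac or blood-pressure effect for Libexin.

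**What to change.** **SAP 7.3.4 and Table 9.16, before database lock:**
1. Replace the within-arm *p-change* with the Levopront minus Libexin difference in change from Day 1 for pulse, systolic and diastolic pressure, adjusted for the Day 1 value, with a 95% CI.
2. Name Day 4 as the main on-treatment contrast. Label the Day 8/ED rows as measured with that day's drug withheld at Day 8; early-termination readings may also be off drug, since protocol 7.5 allows that visit up to Day 3 after the last dose.
3. Add, by arm and visit, the number and percentage of patients whose change or value lies beyond limits that the sponsor fixes in advance. The contrast covers a shift of the whole arm and the counts cover a few affected patients; neither replaces the other.

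**Protocol 3.3.4 and Table 1:** reconcile the two on ECG. If the scheduled ECG is meant as a screening test only, say so.

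**Cost:** some SAP and protocol wording and a few table rows; no new visit, test or patient. Three parameters at two visits give six intervals. If they were independent, the chance that at least one excludes zero with no true effect would be 1 - 0.95⁶ = 26%. Present them as descriptive safety estimates without multiplicity adjustment, not as tests.

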#### **7.3.5 Physical Examination Data**

Physical examination data will be summarized as normal/abnormal data.

Physical examination data will be compared between treatment groups as each time

point using permutation tests.

### 7.3.6 Concomitant Treatments

Concomitant therapy and immunosuppressive therapy during the study time will be summarized by treatment groups. Drugs will be presented by ATC groups as nominal data (absolute and relative frequencies).

### 7.3.7 Listings

Additionally, combined listings from the database will be presented for:

- Laboratory data
- Adverse events and serious adverse events data.

Laboratory data listings will be presented with patient number, age of patient, study period, group of treatment and laboratory data with units and flag of clinically significant abnormalities. Separately the same format listing will be presented for laboratory data but for patients who had abnormal values.

## 7.4 CHANGES IN THE PLANNED ANALYSES

Any changes in the planned statistical methods will be documented and justified in the Clinical Study Report.

## 9. TABLE EXAMPLES

### 9.1 DEMOGRAPHICS AND BASELINE

Table 9.1 Disposition

	Levopront ® (T) n (%)	Libexin ® (C) n (%)
Enrolled subject	xx	xx
Randomized subjects	xx (xx.x%)	xx (xx.x%)
ITT Analysis Set	xx (xx.x%)	xx (xx.x%)
Safety Analysis Set	xx (xx.x%)	xx (xx.x%)
Completed Study per protocol	xx (xx.x%)	xx (xx.x%)
Discontinued prematurely	xx (xx.x%)	xx (xx.x%)
Adverse Event	xx (xx.x%)	xx (xx.x%)
Death	xx (xx.x%)	xx (xx.x%)
Infection of lower respiratory tract	xx (xx.x%)	xx (xx.x%)
Lost to follow-up	xx (xx.x%)	xx (xx.x%)
Consent withdrawn	xx (xx.x%)	xx (xx.x%)
Investigator decision	xx (xx.x%)	xx (xx.x%)
Protocol violation, including non-compliance	xx (xx.x%)	xx (xx.x%)
Protocol entry criteria not met	xx (xx.x%)	xx (xx.x%)
Study is stopped by Sponsor decision	xx (xx.x%)	xx (xx.x%)
Study is stopped by regulatory authorities / ethics committee	xx (xx.x%)	xx (xx.x%)
Other	xx (xx.x%)	xx (xx.x%)
Pregnancy	xx (xx.x%)	xx (xx.x%)

Table 9.2 Demographic and other baseline characteristics.  
ITT analysis set. Screening (baseline). N = xx

Parameter	Levopront ® (T) n (%)	Libexin ® (C) n (%)	p-value
Age (years)			
N	xx	xx	0.xxx
Mean (SD)	xx.x (xx.x)	xx.x (xx.x)	
Median	xx.x	xx.x	
Min - Max	xx.x – xx.x	xx.x – xx.x	
Gender			
Male	xx (xx.x%)	xx (xx.x%)	0.xxx
Female	xx (xx.x%)	xx (xx.x%)	
No data 	xx (xx.x%)	xx (xx.x%)	
Race			
Caucasian	xx (xx.x%)	xx (xx.x%)	
Other	xx (xx.x%)	xx (xx.x%)	
No data 	xx (xx.x%)	xx (xx.x%)	
Height (cm)			
N	xx	xx	---
Mean (SD)	xx.x (xx.x)	xx.x (xx.x)	
Median	xx.x	xx.x	
Min - Max	xx.x – xx.x	xx.x – xx.x	
Weight (kg)			
N	xx	xx	---
Mean (SD)	xx.x (xx.x)	xx.x (xx.x)	
Median	xx.x	xx.x	
Min – Max	xx.x – xx.x	xx.x – xx.x	
BMI (kg/m^2)			
N	xx	xx	0.xxx
Mean (SD)	xx.x (xx.x)	xx.x (xx.x)	
Median	xx.x	xx.x	
Min - Max	xx.x – xx.x	xx.x – xx.x	
Duration of the acute upper respiratory infection (days)			

 Tables in the report may differ from this templates but meaning and information presented should be kept

 if any

 if any

Parameter	Levopront® (T) n (%)	Libexin® (C) n (%)	p-value
N	xx	xx	0.xxx
Mean (SD)	xx.x (xx.x)	xx.x (xx.x)	
Median	xx.x	xx.x	
Min - Max	xx.x – xx.x	xx.x – xx.x	
Duration of dry non-productive cough (days)			
N	xx	xx	0.xxx
Mean (SD)	xx.x (xx.x)	xx.x (xx.x)	
Median	xx.x	xx.x	
Min - Max	xx.x – xx.x	xx.x – xx.x	
Smoking history			
Never smoked			
Currently smokes			
Duration			
N	xx	xx	---
Mean (SD)	xx.x (xx.x)	xx.x (xx.x)	
Median	xx.x	xx.x	
Min - Max	xx.x – xx.x	xx.x – xx.x	
Smoked in the past			
Duration			
N	xx	xx	---
Mean (SD)	xx.x (xx.x)	xx.x (xx.x)	
Median	xx.x	xx.x	
Min - Max	xx.x – xx.x	xx.x – xx.x	
Not known			

Table 9.3 Medical history. ITT analysis set. Screening (baseline). N = xx

MedDRA System Organ Class term MedDRA Preferred term	Levopront® (T) n (%)		Libexin® (C) n (%)	
	x (%)	Y	x (%)	Y
BODY SYSTEM CODE	xx (xx.x)	xx	xx (xx.x)	xx
Term 1	xx (xx.x)	xx	xx (xx.x)	xx
Term 2	xx (xx.x)	xx	xx (xx.x)	xx
...				

Table 9.4 Ongoing diseases/diagnosis/abnormalities. ITT analysis set. Screening (baseline). N = xx

MedDRA System Organ Class term MedDRA Preferred term	Levopront® (T) n (%)		Libexin® (C) n (%)	
	x (%)	Y	x (%)	Y
BODY SYSTEM CODE	xx (xx.x)	xx	xx (xx.x)	xx
Term 1	xx (xx.x)	xx	xx (xx.x)	xx
Term 2	xx (xx.x)	xx	xx (xx.x)	xx
...				

Table 9.5 Previous medication. ITT analysis set. Screening (baseline). N = xx

ATC code Drug	Levopront® (T) n (%)	Libexin® (C) n (%)
Group		
Total	xx (xx.x%)	xx (xx.x%)
DRUG (ATC)	xx (xx.x%)	xx (xx.x%)
...		

 Relative to the informed consent date Relative to the informed consent date

Table 9.6 Physical examination. ITT analysis set. Screening. N = xx

Category	Levopront® (T) n (%) N = XX	Libexin® (C) n (%) N = XX	p-value
Screening (baseline). Day 1			0.xxx
General appearance			
Normal	xx (xx.x%)	xx (xx.x%)	
Abnormal	xx (xx.x%)	xx (xx.x%)	
Not done	xx (xx.x%)	xx (xx.x%)	
Eyes, ears, nose, throat			
Normal	xx (xx.x%)	xx (xx.x%)	
Abnormal	xx (xx.x%)	xx (xx.x%)	
Not done	xx (xx.x%)	xx (xx.x%)	
Neck (including thyroid)			
Normal	xx (xx.x%)	xx (xx.x%)	
Abnormal	xx (xx.x%)	xx (xx.x%)	
Not done	xx (xx.x%)	xx (xx.x%)	

Table 9.7 Vital signs. ITT analysis set. Screening. N = xx

	Levopront® (T) n (%) N = XX	Libexin® (C) n (%) N = XX	p-value
Screening (baseline)			
Body temperature (°C)			0.xxx
N	xx	xx	
Mean (SD)	xx.x (xx.x)	xx.x (xx.x)	
Median	xx.x	xx.x	
Min - Max	xx.x - xx.x	xx.x - xx.x	
Pulse (beats/min)			0.xxx
N	xx	xx	
Mean (SD)	xx.x (xx.x)	xx.x (xx.x)	
Median	xx.x	xx.x	
Min - Max	xx.x - xx.x	xx.x - xx.x	
Respiratory rate (/min)			0.xxx
N	xx	xx	
Mean (SD)	xx.x (xx.x)	xx.x (xx.x)	
Median	xx.x	xx.x	
Min - Max	xx.x - xx.x	xx.x - xx.x	
Systolic blood pressure (Hg mm)			0.xxx
N	xx	xx	
Mean (SD)	xx.x (xx.x)	xx.x (xx.x)	
Median	xx.x	xx.x	
Min - Max	xx.x - xx.x	xx.x - xx.x	
Diastolic blood pressure (Hg mm)			0.xxx
N	xx	xx	
Mean (SD)	xx.x (xx.x)	xx.x (xx.x)	
Median	xx.x	xx.x	
Min - Max	xx.x - xx.x	xx.x - xx.x	

## 9.2 EFFICACY

Table 9.8 Primary efficacy. Daytime cough resolution.

PP analysis set. N = xx

	Levopront® (Test) n (%) N = XX	Libexin® (Control) n (%) N = XX
Daytime cough resolution		
Ongoing ( $\geq 2$ )	xx (xx.x%)	xx (xx.x%)
Resolved ( $< 2$ )	xx (xx.x%)	xx (xx.x%)
Test - Control (resolved)	xx (xx.x%) 97.5% CI [xx.x%; --]	

**Table 9.9 Primary efficacy. Daytime cough resolution.**

ITT analysis set. N = xx

	Levopront® (Test) n (%) N = XX	Libexin® (Control) n (%) N = XX
Daytime cough resolution		
Ongoing (≥2)	xx (xx.x%)	xx (xx.x%)
Resolved (<2)	xx (xx.x%)	xx (xx.x%)
Test – Control (resolved)	xx (xx.x%) 97.5% CI [xx.x%; --]	

**Table 9.10 Secondary efficacy. Nighttime cough resolution.**

ITT population set. N = xx

	Levopront® (Test) n (%) N = XX	Libexin® (Control) n (%) N = XX
Nighttime cough resolution		
Ongoing (≥2)	xx (xx.x%)	xx (xx.x%)
Resolved (<2)	xx (xx.x%)	xx (xx.x%)
p-value (Fisher)	0.xxx	

**Table 9.11 Secondary efficacy. Daytime and Nighttime cough resolution.**

ITT population set. N = xx

	Levopront® (Test) n (%) N = XX	Libexin® (Control) n (%) N = XX
Daytime & Nighttime cough resolution		
Ongoing (≥2)	xx (xx.x%)	xx (xx.x%)
Resolved (<2)	xx (xx.x%)	xx (xx.x%)
p-value (Fisher)	0.xxx	

**Table 9.12 Change in severity and frequency of daytime and nighttime cough on Day 4 and Day 8 from baseline on Day 1. ITT population. N = xx**

	Day 1 (baseline)	Day 4	Change at Day 4	Day 8	Change at Day 8
Levopront®					
Daytime cough					
N	xx	xx	xx	xx	xx
Mean (SD)	xx.x (xx.x)	xx.x (xx.x)	xx.x (xx.x)	xx.x (xx.x)	xx.x (xx.x)
Median	xx.x	xx.x	xx.x	xx.x	xx.x
Min – Max	xx.x – xx.x	xx.x – xx.x	xx.x – xx.x	xx.x – xx.x	xx.x – xx.x
p-change			0.xxx		0.xxx
Libexin®					
Daytime cough					
N	xx	xx	xx	xx	xx
Mean (SD)	xx.x (xx.x)	xx.x (xx.x)	xx.x (xx.x)	xx.x (xx.x)	xx.x (xx.x)
Median	xx.x	xx.x	xx.x	xx.x	xx.x
Min - Max	xx.x – xx.x	xx.x – xx.x	xx.x – xx.x	xx.x – xx.x	xx.x – xx.x
p-change			0.xxx		0.xxx
p-between	0.xxx		0.xxx		0.xxx
Levopront®					
Nighttime cough					
N	xx	xx	xx	xx	xx
Mean (SD)	xx.x (xx.x)	xx.x (xx.x)	xx.x (xx.x)	xx.x (xx.x)	xx.x (xx.x)
Median	xx.x	xx.x	xx.x	xx.x	xx.x
Min - Max	xx.x – xx.x	xx.x – xx.x	xx.x – xx.x	xx.x – xx.x	xx.x – xx.x
p-change			0.xxx		0.xxx
Libexin®					

	Day 1 (baseline)	Day 4	Change at Day 4	Day 8	Change at Day 8
Nighttime cough					
N	xx	xx	xx	xx	xx
Mean (SD)	xx.x (xx.x)	xx.x (xx.x)	xx.x (xx.x)	xx.x (xx.x)	xx.x (xx.x)
Median	xx.x	xx.x	xx.x	xx.x	xx.x
Min - Max	xx.x - xx.x	xx.x - xx.x	xx.x - xx.x	xx.x - xx.x	xx.x - xx.x
p-change			0.xxx		0.xxx
p-between	0.xxx		0.xxx		0.xxx

Figure 9.1 Graphics example

Graphics example

[figure not shown]

Table 9.13 Cough intensity change according to the visual-analogue scale on Day 4 and Day 8 from baseline on Day 1. ITT population. N = xx

	Day 1 (baseline)	Day 4	Change at Day 4	Day 8	Change at Day 8
Levopront®					
Cough intensity. VAS					
N	xx	xx	xx	xx	xx
Mean (SD)	xx.x (xx.x)	xx.x (xx.x)	xx.x (xx.x)	xx.x (xx.x)	xx.x (xx.x)
Median	xx.x	xx.x	xx.x	xx.x	xx.x
Min - Max	xx.x - xx.x	xx.x - xx.x	xx.x - xx.x	xx.x - xx.x	xx.x - xx.x
p-change			0.xxx		0.xxx
Libexin®					

	Day 1 (baseline)	Day 4	Change at Day 4	Day 8	Change at Day 8
Cough intensity. VAS					
N	xx	xx	xx	xx	xx
Mean (SD)	xx.x (xx.x)	xx.x (xx.x)	xx.x (xx.x)	xx.x (xx.x)	xx.x (xx.x)
Median	xx.x	xx.x	xx.x	xx.x	xx.x
Min - Max	xx.x - xx.x	xx.x - xx.x	xx.x - xx.x	xx.x - xx.x	xx.x - xx.x
p-change			0.xxx		0.xxx
p-between	0.xxx		0.xxx		0.xxx

**Table 9.14 Change of FEV1 on Day 8 from baseline values on Day 1.  
ITT population. N = xx**

	Day 1 (baseline)	Day 8	Change at Day 8
Levopront®			
FEV1 (liters)			
N	xx	xx	xx
Mean (SD)	xx.x (xx.x)	xx.x (xx.x)	xx.x (xx.x)
Median	xx.x	xx.x	xx.x
Min - Max	xx.x - xx.x	xx.x - xx.x	xx.x - xx.x
p-change			0.xxx
p-between	0.xxx		0.xxx
Libexin®			
FEV1 (litres)			
N	xx	xx	xx
Mean (SD)	xx.x (xx.x)	xx.x (xx.x)	xx.x (xx.x)
Median	xx.x	xx.x	xx.x
Min - Max	xx.x - xx.x	xx.x - xx.x	xx.x - xx.x
p-change			0.xxx
p-between	0.xxx		0.xxx
Levopront®			
FEV1 (%)			
N	xx	xx	xx
Mean (SD)	xx.x (xx.x)	xx.x (xx.x)	xx.x (xx.x)
Median	xx.x	xx.x	xx.x
Min - Max	xx.x - xx.x	xx.x - xx.x	xx.x - xx.x
p-change			0.xxx
p-between	0.xxx		0.xxx
Libexin®			
FEV1 (%)			
N	xx	xx	xx
Mean (SD)	xx.x (xx.x)	xx.x (xx.x)	xx.x (xx.x)
Median	xx.x	xx.x	xx.x
Min - Max	xx.x - xx.x	xx.x - xx.x	xx.x - xx.x
p-change			0.xxx
p-between	0.xxx		0.xxx

